2 LIST OF ABBREVIATIONS

Abbreviation	Definition
AE	Adverse Event
AEoSI	Adverse Event of Special Interest
ATC	Anatomical Therapeutic Chemical
Bayley-III	Bayley Scale of Infant and Toddler Development®- Third Edition
BH4	Sapropterin dihydrochloride
BMI	Body Mass Index
CDC	Centers for Disease Control and Prevention
CI	Confidence interval
CRF	Case Report Form
CSR	Clinical Study Report
ECG	Electrocardiogram
FSIQ	Full Scale IQ
HLGT	High level group term
IDC	Index of Dietary Control
IP	Investigational Product
IQ	Intelligence Quotient
MedDRA	Medical Dictionary for Regulatory Activities
Phe	Phenylalanine
PKU	Phenylketonuria
SAE	Serious Adverse Event
SAP	Statistical Analysis Plan
SD	Standard Deviation
SOC	System Organ Class
TEAE	Treatment-Emergent Adverse Event

	SAP PKU-015, Version 3.0	Page 5 of 31
---	--------------------------	--------------

Abbreviation	Definition
WISC-IV	Wechsler Intelligence Scale for Children®-Fourth Edition
WHO	World Health Organization
WHODrug	World Health Organization Drug Dictionary
WPPSI-III	Wechsler Preschool and Primary Scale of Intelligence™-Third Edition

	SAP PKU-015, Version 3.0	Page 6 of 31
---	--------------------------	--------------

3 INTRODUCTION

BioMarin PKU-015 is a 2-part multicenter, open-label study designed to evaluate the safety of Kuvan and its effect on neurocognitive function, blood Phe concentration, and growth in children with PKU who are 0-6 years old at study entry. The purpose of this document is to provide specific details of the statistical analysis methods and data presentations collected in Protocol PKU-015 protocol amendment 2 (dated November 30, 2010) for the Neurocognitive Study (Part 2). This excludes the analyses for substudy 1 and substudy 2, which were outlined in a separate statistical analysis plan document.

If discrepancies exist between the text of the statistical analysis as planned in the protocol and the final SAP, a protocol amendment will not be issued and the SAP will prevail.

3.1 Objectives of Study

The primary objective of the study is:

- To evaluate the long-term efficacy of Kuvan on preserving neurocognitive function in children with PKU when treatment is initiated at 0-6 years at Screening

The secondary objectives of the study are:

- To evaluate the long-term safety of Kuvan in the study population
- To evaluate the effect of Kuvan on growth parameters in the study population

3.2 Study Design

This 2-part, multicenter, open-label study is designed to evaluate the safety of Kuvan and its effect on neurocognitive function, blood Phe concentration, and growth in children with PKU when treatment is initiated at 0-6 years of age. The study will be considered complete when approximately 45 subjects have completed 7 years of treatment.

One of the goals of the study will be to decrease blood Phe levels to reach a goal of ≤ 240 $\mu\text{mol/L}$. Subjects will meet with a dietician at each study visit to review dietary Phe intake. Dietary Phe may be added to the diet, at the discretion of the Investigator, if a blood Phe level falls below 120 $\mu\text{mol/L}$ or decreased if blood Phe level is above 240 $\mu\text{mol/L}$. If a subject's blood Phe falls below 120 $\mu\text{mol/L}$, at the discretion of the investigator, a gradual increase of approximately 5-20 mg/kg of Phe supplement may be added to the diet. If a subject's blood Phe level goes above 240 $\mu\text{mol/L}$, dietary Phe may be decreased by

	SAP PKU-015, Version 3.0	Page 7 of 31
---	--------------------------	--------------

approximately 5 to 20 mg/kg or defined by the standard used at each treatment center, at the discretion of the investigator.

Part 1: Evaluation of Kuvan Responsiveness

Beginning at Week 0 and after all baseline assessments are completed, subjects enrolled into the study will receive 20 mg/kg Kuvan daily for 4 weeks. Subjects will return to the clinic weekly for safety assessments and blood Phe concentration measurement. Subjects should continue with their current amount of dietary Phe intake. However, if a subject's blood Phe concentration drops below 120 $\mu\text{mol/L}$, at the discretion of the Investigator, a gradual increase by approximately 5 to 20 mg/kg of daily dietary Phe supplement may be added to the diet. It is important to avoid unstable swings in blood Phe concentrations. No dose adjustments can be made during Part 1 without consultation with the Medical Monitor.

Part 2: Neurocognitive Study

Subjects who are responsive to Kuvan will continue to receive once a day doses of 20 mg/kg Kuvan orally. A Kuvan-responsive subject is defined as a subject with $\geq 30\%$ average reduction in blood Phe concentration calculated by the mean of the weekly percent change from baseline in blood Phe concentration at Weeks 1, 2, 3 and 4. The baseline blood Phe concentration is calculated as the mean of the results from Screening visit and at Week 0 (prior to dosing with Kuvan). At the discretion of the Investigator, the subject's daily Phe intake may be modified if blood Phe concentration falls below 120 $\mu\text{mol/L}$ during the study. Kuvan dose may also be reduced after Week 5 after consultation with the Medical Monitor, in subjects who do not tolerate the 20 mg/kg/day dose.

Neurocognitive testing will be performed within 6 weeks of determination of Kuvan responsiveness in all Kuvan-responsive subjects. The types of neurocognitive tests used (Bayley Scales of Infant and Toddler Development®-Third Edition [Bayley-III], Wechsler Preschool and Primary Scale of Intelligence™-Third Edition [WPPSI-III], and/or Wechsler Intelligence Scale for Children®-Fourth Edition [WISC-IV]) will be those appropriate for the subject's current age at assessment. Table 3.2.1 shows the neurocognitive test to be used according to subject age.

	SAP PKU-015, Version 3.0	Page 8 of 31
---	--------------------------	--------------

Table 3.2.1: Neurocognitive Assessments

Age Group	Infancy	Preschool		School-Age
Assessment	Bayley-III	WPPSI-III (First Form)	WPPSI-III (Second Form)	WISC-IV
Age	0 months through < 30 months	30 months through < 4 years	≥ 4 years through < 7 years	≥ 7 years and older
Frequency	Every 6 months ± 2 weeks	Once a year ± 2 weeks	Once a year ± 2 weeks	Every 2 years ± 2 weeks

Growth, blood Phe concentration, and safety will be monitored. These and the neurocognitive assessments will be performed every 6 to 24 months, depending on the type of assessment, until the end of the study.

3.3 Study Population

Individuals eligible to participate in this study must meet all of the following criteria:

- Parent(s) or guardian(s) willing and able to provide written, signed informed consent after the nature of the study has been explained, and prior to any research-related procedures.
- Parent(s) or guardian(s) willing and able to comply with all study procedures.
- Female subjects of childbearing potential (as determined by the investigator) and sexually mature male subjects willing to use a medically accepted method of contraception throughout the study. Female subjects of childbearing potential willing to undergo periodic pregnancy tests during the course of the study
- Established diagnosis of PKU with hyperphenylalaninemia (HPA) documented in the medical record by at least 2 blood Phe concentrations $\geq 360 \mu\text{mol/L}$ (6 mg/dL) taken at least 3 days apart
- Documented blood Phe control (defined by the standard used at each treatment center) prior to study enrollment, if applicable (eg, the subject is old enough for these data to be collected); blood Phe concentrations for subjects < 6 months old at Screening must be considered controlled and stable by the Investigator

	SAP PKU-015, Version 3.0	Page 9 of 31
---	--------------------------	--------------

- Willing to adhere to a prescribed Phe-restricted diet in order to maintain blood Phe concentrations within the recommended ranges established at the subject's study site
- Age 0 to 6 years, inclusive, at Screening

Individuals eligible to participate in Part 2: Neurocognitive Study must meet **all** of the following criteria:

- Completion of Week 4 visit in Part 1
- Responsive to Kuvan during Part 1, defined as a $\geq 30\%$ average reduction in blood Phe concentration calculated as the mean of the weekly percent change from baseline in blood Phe concentration at Weeks 1, 2, 3, and 4
- Bayley-III or IQ test score ≥ 80 when tested within 6 weeks of determination of Kuvan responsiveness in Kuvan-responsive subjects

Individuals who meet any of the following exclusion criteria will not be eligible to participate in the study:

- Has known hypersensitivity to Kuvan or its excipients
- Use of Kuvan or any investigational product or investigational medical device within 30 days prior to screening, or requirement for any investigational agent prior to completion of all scheduled study assessments
- Concurrent disease or condition that would interfere with study participation or safety (eg, seizure disorder, oral steroid-dependent asthma or other condition requiring oral or parenteral corticosteroid administration, or insulin-dependent diabetes)
- Use of phosphodiesterase type 5 inhibitor, often shortened to PDE5 inhibitor (eg, sildenafil citrate, vardenafil, tadalafil, avanafil, lodenafil, mirodenafil, udenafil)
- Any condition that, in the view of the PI, places the subject at high risk of poor treatment compliance or of not completing the study
- Established diagnosis of primary tetrahydrobiopterin (BH4) deficiency
- History of organ transplantation
- Perceived to be unreliable or unavailable for study participation or to have parents or legal guardians who are perceived to be unreliable or unavailable

	SAP PKU-015, Version 3.0	Page 10 of 31
---	--------------------------	---------------

- Use of methotrexate or other medications that inhibit folate metabolism
- Serious neuropsychiatric illness (eg, major depression) not currently under medical control

3.4 Sample Size Determination

The sample size calculation assumes each child will have 2 post-treatment test results from the WPPSI-III and /or WISC-IV tests at least 2 years apart. The goal is to exclude a mean 2.5-point loss per year in IQ score. Given a 2-side Type I error rate of 0.05, if the mean IQ score at baseline is 100, the standard deviation is no larger than 16, and the correlation between the 2 test results is 0.8, a sample size of 45 subjects will yield at least 90% power.

To account for the possibility of dropouts and to have reasonable precision for estimating change in IQ from the time a child reaches at least age 30 months until the end of the study, approximately 60-80 Kuvan-responsive subjects will be enrolled in the study.

3.5 Blinding and Randomization Methods

This is an open-label study. No blinding and randomized treatment allocations were used in this study.

3.6 Interim Analysis

There is no formal interim analysis planned. However, an analysis of data for a subset of subjects who responded to sapropterin therapy and had completed at least 2 years in the study as of June 2012, including subjects who terminated early from the study prior to reaching their 2-year study visit, was performed. Neurocognitive function, blood and dietary Phe control, growth assessments, and adverse events were examined.

4 GENERAL ANALYSIS CONSIDERATION

Continuous endpoints will be summarized using descriptive statistics such as the number of observations, mean, standard deviation, median, minimum, maximum, 25th percentile, and 75th percentile. Categorical endpoints will be summarized by the frequency and percent.

The last available measurement or procedure performed prior to initial study drug administration will be considered the baseline measurement or procedure for analysis purpose, unless otherwise specified.

All tests will be conducted at a two-sided alpha level of 0.05, and all confidence intervals will be given at a two-sided 95% level, unless stated otherwise.

No multiplicity adjustment will be made. Data from all sites will be pooled; no by-site analysis will be performed.

4.1 Analysis Populations

The Full Analysis set (FAS) will consist of all subjects who enroll into the study.

The Enrolled population will consist of all subjects who enter Part 2 of the study and met the inclusion/exclusion criteria per CRF. This population involves subjects who respond to Kuvan and had a Bayley-III or IQ test score ≥ 80 within 6 weeks of determination of Kuvan responsiveness in Part 1. Kuvan responders consist of all subjects with at least 30% average reduction in blood Phe concentration calculated as the mean of the weekly percent change from baseline at Week 1, 2, 3 and 4 in Part 1.

The Efficacy population will consist of all subjects from the Enrolled population who have at least two WPSI/WISC assessments.

The Safety population will consist of all subjects who have received any study drug in the FAS population.

4.2 Treatment Group Presentation

All subjects enrolled into the study will be administered 20 mg/kg Kuvan daily.

Efficacy and safety analysis results will be presented by age group at enrollment, and all ages combined except for the Neurocognitive summary. The following age groups will be used for all subjects enrolled in Part 2:

- 0 – 1 year old (0 to < 1)

	SAP PKU-015, Version 3.0	Page 12 of 31
---	--------------------------	---------------

- 1 - 2 years old (≥ 1 to < 2)
- 2 - 4 years old (≥ 2 to < 4)
- 4 – 6 years old (≥ 4 to < 7)

In addition, safety analysis may also be presented during Part 1 by the following group:

- Part 2 Enrolled
- Part 2 Not Enrolled
- Overall

4.3 Pooling of Data from Sites with Small Enrollment

Since the enrollment for each site is expected to be small, the analyses will not be adjusted by site or pooled sites.

4.4 Study Day Derivation

Study Day 1 is used as the reference date for the derivation of Study Day in data analyses and displays, and is defined as the first date study drug is administered in Part 1. Study Day is computed by subtracting the Study Day 1 date from the visit date and plus 1 if the visit date occurs on or after the first study drug administration date. Otherwise, Study Day will be the visit date minus the Study Day 1 date. There is no Study Day 0. For specific efficacy analyses, Study Day 1 may also be defined as the day of the first neurocognitive assessment.

4.5 Visit Window for Analysis

The baseline blood Phe concentration is defined as the mean of the screening and Week 0 (prior to dosing with Kuvan) result. Baseline measurement for other assessments is defined as the latest non-missing measurement prior to the first study drug administration in Part 1. If there are two or more measurements within an analysis visit window, the measurement that is closest to the scheduled time point will be used for analyses. If the two closest measurements to the scheduled time point are equidistant from that scheduled analysis time point, the average (or more conservative) of the two assessments will be used for analyses.

Table 4.5.1 presented below defines visit windows for the scheduled analysis time points by analysis parameter.

	SAP PKU-015, Version 3.0	Page 13 of 31
---	--------------------------	---------------

Table 4.5.1: Visit Windows

Assessment	Scheduled Time Point	Visit Window
Bayley-III	Baseline	First measurement date after determination of Kuvan responsiveness (Day 30 to Day 120)
	Month 6	Day 121 to Day 273
	Month 12	Day 274 to Day 456
	Month 18	Day 457 to Day 638
	Month 24	Day 639 to Day 821
WPPSI-III, WISC-IV (based on Month 2 occurrence)	Baseline	First measurement date after determination of Kuvan responsiveness at Month 2 visit (Day 30 to Day 120)
	Month 12	Day 121 to Day 548
	Month 24	Day 549 to Day 913
	Month 12 *i , where $i=2,3,4,5,6,7,\dots$	Day $365*i - 181$, Day $365*i + 183$
WPPSI-III, WISC-IV (based on first assessment)	Baseline*	First measurement date after determination of Kuvan responsiveness
	Month 12	Day 2 to Day 548
	Month 24	Day 549 to Day 913
	Month 12 *i , where $i=2,3,4,5,6,7,\dots$	Day $365*i - 181$, Day $365*i + 183$
Height, head circumference, physical exam	Baseline	Last measurement date prior to the initial study drug administration
	Week 4	Day 2 to 76
	Month 3	Day 77 to Day 137
	Month 6	Day 138 to Day 273
	Month 12	Day 274 to Day 456

	SAP PKU-015, Version 3.0	Page 14 of 31
---	--------------------------	---------------

Assessment	Scheduled Time Point	Visit Window
	Month 18	Day 457 to Day 638
	Month 24	Day 639 to Day 821
	Month 6*i, where i=2,3,4,5,6,7,...	Day $\text{round}(182*i + i/2) - 91$, Day $\text{round}(182*i + i/2) + 91 - \text{mod}(i,2)^*$
Tryptophan, tyrosine	Baseline	Last measurement date prior to the initial study drug administration
	Week 4	Day 2 to 76
	Month 3	Day 77 to Day 137
	Month 6	Day 138 to Day 273
	Month 12	Day 274 to Day 548
	Month 24	Day 549 to Day 913
	Month 12*i, where i=2,3,4,5,6,7,...	Day $365*i - 181$, Day $365*i + 183$
	Blood Phe level, Dietary Phe, Weight, Vital Signs	Baseline
Week 1		Day 2 to Day 11
Week 2		Day 12 to Day 18
Week 3		Day 19 to Day 25
Week 4		Day 26 to Day 42
Month 2		First measurement date after determination of Kuvan responsiveness (Day 43 to Day 76)
Month 3		Day 77 to Day 106
Month 4		Day 107 to Day 137
Month 5		Day 138 to Day 167
Month 6		Day 168 to Day 273

	SAP PKU-015, Version 3.0	Page 15 of 31
---	--------------------------	---------------

Assessment	Scheduled Time Point	Visit Window
	Month 12	Day 274 to Day 456
	Month 18	Day 457 to Day 638
	Month 6*i, where i=2,3,4,5,6,7,...	Day $\text{round}(182*i + i/2) - 91$, Day $\text{round}(182*i + i/2) + 91 - \text{mod}(i,2)^*$
Additional Week 0 Vital signs	15 min postdose	1 min to 22 min elapsed time
	30 min postdose	23 min to 37 min elapsed time
	45 min postdose	38 min to 52 min elapsed time
	60 min postdose	53 min to 75 min elapsed time
	90 min postdose	76 min to 105 min elapsed time
	120 min postdose	106 min to 150 min elapsed time
	180 min postdose	151 min to 360 min elapsed time
Clinical laboratory tests	Baseline	Last measurement date prior to the initial study drug administration
	Week 1	Day 2 to Day 15
	Week 3	Day 16 to Day 25
	Week 4	Day 26 to Day 42
	Month 2	First measurement date after determination of Kuvan responsiveness (Day 43 to Day 76)
	Month 3	Day 77 to Day 106
	Month 4	Day 107 to Day 137
	Month 5	Day 138 to Day 167
	Month 6	Day 168 to Day 273
	Month 12	Day 274 to Day 456
	Month 18	Day 457 to Day 638
	Month 6*i, where i=2,3,4,5,6,7,...	Day $\text{round}(182*i + i/2) - 91$, Day $\text{round}(182*i + i/2) + 91 - \text{mod}(i,2)^*$

*Baseline refers to first assessment for this visit windowing

	SAP PKU-015, Version 3.0	Page 16 of 31
---	--------------------------	---------------

4.6 Multiplicity Adjustment

Not applicable.

4.7 Handling of Dropouts and Missing Data

Subjects who discontinued prematurely will not be replaced. Missing dates or partially missing dates will be imputed conservatively for concomitant medications and AEs to ensure that an AE is considered treatment emergent and has the longest possible duration.

For the efficacy endpoints, the missing data will not be imputed.

5 SUBJECT DISPOSITION

The following disposition information will be summarized by age group at enrollment and all ages combined:

- Number of subjects enrolled in Part 1 and continue to Part 2
- Number of subjects who completed the study and each Part
- Number of subjects who discontinued the study and each Part
- Number of subjects in each analysis population

The number and percentage of subjects who terminated early will be summarized separately by age group at enrollment, and all ages combined. The reasons for early termination will also be summarized and provided in the same summary table. A subject listing of completion and early termination will be provided.

6 PROTOCOL DEVIATIONS

A major protocol deviation is defined as a departure from the approved study protocol that may impact the rights, safety, or welfare of the subjects or the integrity of the data, which will be summarized by deviation category.

A minor or administrative protocol deviation is defined as a departure from the approved study protocol that has minimum or no impact on the rights, safety, or welfare of the subjects or the integrity of the data. Minor protocol deviations will also be summarized by deviation category. For details regarding the classification of the deviations, please refer to the Protocol Deviation Plan.

	SAP PKU-015, Version 3.0	Page 17 of 31
---	--------------------------	---------------

The number and percentage of subjects with major protocol deviations and type of deviation will be summarized by age group at enrollment, and all ages combined in the Enrolled population. A summary of the inclusion/exclusion criteria deviations, including exemptions, and protocol deviations will be provided. In addition, a list of subjects enrolled who did not meet the entrance eligibility criteria and subjects who did not adhere to the protocol after entry will be provided.

7 DEMOGRAPHICS AND BASELINE CHARACTERISTICS

Subject demographics (age, sex, ethnicity, and race) and baseline characteristics (weight, height, head circumference, blood Phe concentration, prescribed dietary Phe, and blood tryptophan and tyrosine concentration) will be summarized separately by age group at enrollment and all ages combined. A separate table will summarize the neurocognitive testing (Bayley-III, WPPSI-III and WISC-IV) at Month 2 in Part 2.

Age, sex, ethnicity, and race will be summarized using the number and percentage of subjects with a particular attribute. The denominators for percentages will be based on the number of subjects in each age group. Weight, height, head circumference, blood Phe concentration, blood tryptophan and tyrosine concentration, and neurocognitive tests will be summarized using descriptive statistics including n, mean, SD, median, min, max, 25th percentile, 75th percentile. In addition, the percentile and z-scores of weight, height, and head circumference based on CDC Clinical Growth Charts (WHO Growth Charts for subjects less than 2 years of age) will be summarized using descriptive statistics.

A subject listing of demographics and baseline characteristics will also be provided.

8 MEDICAL HISTORY

Each subject's chronic diseases, disorders, and surgeries in the past will be collected as general medical history. General medical history will be summarized using MedDRA by system organ class (SOC) and medical history by descending order of frequency for all subjects in the Enrolled and Safety populations. A by-subject listing of each subject's medical history collected at the Screening Visit will also be provided.

9 PRIOR AND CONCOMITANT MEDICATIONS/PROCEDURES

Prior and concomitant medications will be summarized across all subjects and by age group in the Enrolled and Safety populations. For analysis purposes, the following definitions will be used to determine prior and concomitant medications:

	SAP PKU-015, Version 3.0	Page 18 of 31
---	--------------------------	---------------

- Prior medications: any medications taken within 30 days prior to screening and prior to the date of initial study drug administration in Study PKU-015.
- Concomitant medications: any medications initially taken on or after the date of initial study drug administration in Part 1.
- Prior and concomitant medications: any medications taken both prior to the date of initial study drug administration and on or after the date of initial study drug administration in Part 1 will be reported both as prior and concomitant medications. Therefore, any medications taken prior to the first date of Part 1 where the stop date is reported as “continuing” or missing will be considered both as prior and concomitant medications.

In the event the start date of a medication is completely missing, the start date will be imputed as the first dose date if the stop date is in the same year or later than the first dose date.

In the event the start date of a medication is partial, the following imputation rules will be applied:

- If only day is missing and year and month is after the first dose year and month, then the start date will be imputed as the first day of the month. If only day is missing and the year and month is prior to the first dose year and month, then the start date will be imputed as the last day of the month. If month is the same as the month of first dose of study drug then the start date will be imputed as the first dose date.
- If only year is non-missing, then the start date will be imputed as the first day of the year if the year is after the year of first dose. If year is the same as the year of first dose of study drug then the start date will be imputed as the first dose date. If year is before the year of first dose of study drug then the start date will be imputed to the first day of July of the year.

In the event the stop date of a medication is partial, the following imputation rules will be applied:

- If only day is missing, then the end date will be imputed as the last day of the month.
- If only year is non-missing, then the end date will be imputed as the last day of the year.

All medications will be coded using the current version of the World Health Organization Drug (WHO Drug) dictionary at program termination or annual reporting. Prior and concomitant medication use will be separately summarized by Anatomical Therapeutic

	SAP PKU-015, Version 3.0	Page 19 of 31
---	--------------------------	---------------

Chemical (ATC) medication class (Level 4) and preferred name (ie, generic medication name). Concomitant medication use will also be summarized. A subject reporting the same medication more than once will be counted once when calculating the number and percentage of subjects who received that medication. A by subject listing of each subject’s prior and concomitant medications will be provided.

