14.1 Adverse Events

14.1.1 All Adverse Events

Adverse events will be coded in accordance with the most current version of MedDRA at program termination or annual reporting. Only treatment-emergent adverse events (TEAEs) occurring and reported during the study will be included in the adverse event summaries. A TEAE is defined as any AE that newly appeared or worsened in severity following initiation of the study drug administration. If the onset date of an AE is missing, the AE will be considered treatment-emergent. The incidence of all treatment-emergent AEs will be summarized by system organ class (SOC), preferred term (PT), relationship to study drug and CTCAE grades. For those AEs that occurred more than once, regardless of study part, the maximum severity will be used to summarize the AEs by severity.

If the onset date or end date of an adverse event is partial, the same imputation rules described in section 9 will be applied.

The treatment-emergent AEs will be summarized in the following categories:

- All AEs by SOC and preferred term
- All AEs by preferred term in descending frequency order
- All AEs by SOC, preferred term, and NCI CTCAE grade
- AEs assessed by investigators as related to study drug by SOC and preferred term
- AEs assessed by investigators as related to study drug by SOC, preferred term and NCI CTCAE grade
- Serious AEs (SAEs) by SOC and preferred term
- All SAEs by preferred term in descending frequency order

	SAP PKU-015, Version 3.0	Page 27 of 31
---	--------------------------	---------------

- SAEs assessed by investigators as related to study drug by SOC and preferred term
- Death
- AEs leading to withdrawal from study by SOC and preferred term
- AEs leading to study drug discontinuation by SOC and preferred term

A summary of all AEs and adverse event listings will also be provided.

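### SAP Section 9 can impute a start date later than a known stop date, so medications that ended before first dose are classed as concomitant; Section 14.1.1 opens the same gap for adverse events

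*SAP*

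**What the plan says.** Three branches of SAP Section 9 move a medication start to the first dose date.

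- **Start completely missing:** the start is "imputed as the first dose date if the stop date is in the same year or later than the first dose date".
- **Day missing:** the condition on the month reads "the same as the month of first dose of study drug then the start date will be imputed as the first dose date".
- **Year only:** "If year is the same as the year of first dose of study drug then the start date will be imputed as the first dose".

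Two further branches handle starts before the dosing period. A day-missing start in an earlier month goes to the last day of that month, and a year-only start in an earlier year goes to 1 July of that year.

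Section 9 defines concomitant medications as "any medications initially taken on or after the date of initial study drug administration in Part 1".

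For adverse events, Section 14.1.1 says: "If the onset date or end date of an adverse event is partial, the same imputation rules described in section 9 will be applied." It has its own rule for absent onsets: "If the onset date of an AE is missing, the AE will be considered treatment-emergent." The same section defines a treatment-emergent event as "any AE that newly appeared or worsened in severity following initiation of the study drug administration".

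Section 4.7 gives the purpose. Imputation is meant to be conservative, so that an adverse event counts as treatment-emergent and is given its greatest possible length.

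**The concern.** The first branch consults the stop date, but only by calendar year. The other two first-dose branches do not consult it at all. Nothing in Section 9 keeps an imputed start from passing a known stop, and nothing says that a record which ended before first dose is prior only. Programmed as written, the rules therefore return an impossible interval and a wrong classification for records whose timing relative to first dose is already known from the stop date. This is a stated rule giving a wrong answer, not an omitted detail.

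The prior and concomitant medication tables are at stake. The adverse event tables are too, if pre-dose events are captured. Under Section 14.1.2, time at risk for an event of special interest ends at the event start. For a Part 2 subject, a resolved pre-dose event with its onset moved to first dose would add one to the numerator and leave that subject almost no time in the denominator.

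**Working it through.** The plan states no figure on this point, so there is none to reproduce. The check applies the Section 9 start rules literally to test dates.

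**Inputs.** The rules are those of Section 9. The dates are illustrative assumptions, with first dose on 15 June 2011. Section 9 gives no duration formula for medications, so length is taken as stop − start + 1, the form Section 11 uses for dosing periods.

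**Branches that impute to first dose**

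| Recorded start | Known stop | Imputed start | Stop − start + 1 | Start on or after first dose? |
|---|---|---|---|---|
| missing | 10 Mar 2011 | 15 Jun 2011 | −97 + 1 = −96 days | yes |
| Jun 2011 | 10 Jun 2011 | 15 Jun 2011 | −5 + 1 = −4 days | yes |
| 2011 | 10 Mar 2011 | 15 Jun 2011 | −97 + 1 = −96 days | yes |
| missing | 20 Dec 2010 | not imputed | – | – |
| missing | 20 Jul 2011 | 15 Jun 2011 | 35 + 1 = 36 days | yes, validly |

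In the first three rows the start follows the stop, and the imputed start meets the concomitant definition although the medication ended before dosing. The last two rows mark the limits: a stop in an earlier year triggers no imputation, and a stop after first dose gives a proper interval.

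**Is this an accident of the dates chosen?** Every pre-dose stop in the dosing year was run for three assumed first-dose dates.

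| First dose | Missing-start rule | Year-only rule | Same-month rule |
|---|---|---|---|
| 15 Jan | 14/14 | 14/14 | 14/14 |
| 15 Jun | 165/165 | 165/165 | 14/14 |
| 15 Dec | 348/348 | 348/348 | 14/14 |

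Each cell counts pre-dose stops for which the imputed start falls after the stop. The same-month column uses only stops in the month of first dose. The error occurs every time. The counts show that the rule is deterministic; they do not show how often such records arise.

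**Branches for earlier periods**

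- Start May 2011, stop 10 May 2011: imputed 31 May; 10 − 31 + 1 = −20 days.
- Start 2010, stop 10 Mar 2010: imputed 1 Jul 2010; −113 + 1 = −112 days.

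These intervals are also impossible, but the imputed start stays before first dose, so the record remains prior. The branch for a later month does not fail: start Jul 2011 with stop 10 Jul 2011 is imputed to 1 Jul, length 10 days.

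**Adverse events.** Two routes must be kept apart. A partial onset takes the Section 9 partial-date rules, so onset in the month or year of first dose goes to the first dose date whatever the end date. A completely missing onset is treatment-emergent by Section 14.1.1 itself, which imputes no date. On either route an event with a known end before first dose is counted as treatment-emergent, although it can neither have appeared nor have worsened after dosing began. That contradicts the section's own definition.

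**The case against.** The best defence is that over-counting is deliberate: Section 4.7 declares a conservative aim, and the safety analyses are descriptive. That stands where timing is unknown. It does not reach a record whose known stop rules out a start on treatment, and a start after the stop defeats the aim of the greatest possible length.

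Four stronger readings are tempting, and the SAP does not support them.

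- *About half of same-year records with a missing start are affected.* This needs stop dates spread evenly over the year. Section 9 counts as prior only medications taken within 30 days before screening, so relevant pre-dose stops fall in a short window whose length depends on a screening period the SAP does not give. Stops such as 10 March in the example (97 days before dosing) may well lie outside it. On-study medications can stop at any time over years of treatment.
- *The missing-start rule also governs adverse events.* Section 14.1.1 imports Section 9 only for partial dates, so a missing onset produces no start after a stop.
- *Pre-dose events will be reported as treatment-emergent.* This holds only if they are recorded as adverse events. The SAP does not say so, and Section 8 places past disorders in medical history.
- *Negative durations will distort the tables.* The planned medication and adverse event summaries count subjects and incidence, not duration. A negative value would appear at most in a listing.

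**Conclusion.** The point holds and is minor. For medications it follows from the text alone: a missing start with a stop earlier in the dosing year, or a partial start in the month or year of first dose with a stop before first dose, yields a start after the stop and a concomitant label for a medication that had ended. In the earlier-month and earlier-year branches only the interval is wrong; the prior classification is right. For adverse events the consequence is conditional on pre-dose events being collected, and it is confined to events with a partial or missing onset and a known end before first dose.

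The number of such records cannot be derived from the SAP and is probably small. The primary endpoint and all other efficacy analyses are unaffected.

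**What to change.** In Section 9, add for every start-date rule, not only the three that impute to first dose:

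1. An imputed start may not be later than a known stop date.
2. A record whose stop is before first dose, whether complete or partial but clearly earlier, is prior only.

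In Section 14.1.1, add that an adverse event with a missing or partial onset is treatment-emergent unless its end date is before first dose.

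Records whose timing relative to first dose is truly unknown keep the present conservative default. With the first rule, each failing example above takes the stop date as its start and has length 1 day instead of a negative value. The cost is three sentences and a short check in the date-imputation code; no further data are needed.
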